 - Single pulse TMS has been associated with seizure in two persons who had risk factors for seizure such as taking medications that lower the seizure threshold and having a relative with epilepsy. One normal subject who did not have risk factors for seizure and who was not taking medication either had a seizure or a syncopal episode during a single pulse TMS study^{27, 43}.
 - A seizure caused by rTMS could place subjects at financial risk secondary to cost of medical care. Having a seizure might also influence driving privileges, employment, and the ability to obtain

insurance. Subjects are informed of these risks in the consent process.

- Effects on Cognition: Few adverse effects of rTMS on cognition have been reported⁴⁴ and there is a trend for performance to be better on measures such as delayed story recall. Using rTMS, two studies, reported possible adverse effects lasting up to one hour. Greenberg et al. (cited in Wasserman⁴¹) reported that task switching was impaired after 20-Hz stimulation of the right compared to the left dorsolateral frontal lobe⁴⁵. Flitman et al⁴⁶ reported a significant decrease in logical memory one hour after testing after extensive stimulation using parameters that exceed guidelines for inter-train interval (150 trains of rTMS at 15 Hz, 750 msec duration, and 1.2 times the MEP).
- Effects on Mood: Dysphoria with crying has been induced after left prefrontal stimulation⁴⁷. In contrast, high-frequency stimulation of the right prefrontal cortex may transiently improve mood as rapid-rate rTMS has been shown to be a safe and effective treatment in patients with depression.
- Effects on Hearing: Foam earplugs were effective in avoiding changes in the auditory threshold in a safety study of TMS⁴⁴.

Protection Against Risks: Repetitive Transcranial Magnetic Stimulation

Transcranial magnetic stimulation will be delivered by fully trained study personnel.

The following steps will be taken to minimize the risks discussed above. Additionally, subject exclusion criteria should eliminate subjects for whom risk is greater.

1. First subjects are fully informed of all risks during the informed consent process. We use stimulation procedures that fall within the guidelines recommended at the conclusion of the NIH Panel on TMS (see Wasserman⁴¹). Patients will be fully informed of the possibility of seizure, the plan for care in event of a seizure, and any foreseeable financial or medical consequences resulting from a seizure.
2. All subjects will wear ear plugs during testing sessions. TMS will be stopped if an ear plug falls out during a session.
3. A study physician trained in rescue procedures, will be on call when a subject is receiving single pulse TMS in this study. The study physician will be called by study personnel in the event of muscle contractions persisting after TMS (possible seizure) or complaints of dizziness, nausea, shortness or loss of breath, or loss of consciousness (possible syncope). Study personnel will note body parts that might be affected (e.g., the left arm or leg after right hemisphere stimulation) and/or other symptoms that might occur and report them to the

Version 10 Revised 11/21/2014

study physician. [Should these be observed, the session will be terminated, and the subject will not be tested again].

4. If a subject were to have a seizure or syncopal episode during or immediately following TMS, the following precautions will be performed by study personnel:
 - a. The stimulator will be stopped and the coil will be removed from the subject's head.
 - b. The subject will be supported to physically guard against injury.
 - c. The subject will be placed on his/her side on a flat surface away from sharp edges.
 - d. The study physician will be called.
 - e. Emergency services will be called by study personnel to transport the subject to the emergency room if so directed by the study physician.
 - f. Emergency services will be called if the study physician cannot be reached.
 - g. Either the study physician or the PI or subinvestigators will accompany the subject to the ER and explain the recommended post-event assessment which is as follows:

It is recommended that after the seizure is over, the subject will be examined thoroughly for injuries and a complete neurological exam will be completed. Routine studies, including calcium, magnesium, and prolactin, will be completed and urine will be sent for a drug screen. An MRI scan of the head will be performed to rule out underlying epileptogenic pathology. An EEG will be performed with hyperventilation and anterior temporal leads. The subject will be advised that following a seizure provoked by TMS, the likelihood of further spontaneous seizures is not significantly increased unless other pathology is discovered. The subject will be scheduled for a neurology consultation. The subject will not be allowed to drive himself/herself home. Transportation would be arranged for the subject.

The PIs and study physician would provide documentation that the seizure happened during a TMS session, that it does not constitute epilepsy, and that seizures caused by TMS have not resulted in future seizures. Seizures induced during electroconvulsive therapy (ECT) for depression, for example, do not cause driving privileges to be revoked in the state of Arkansas. Like ECT, a seizure occurring after TMS would not cause driving privileges to be revoked.

Benefits

Potential benefits to subjects participating in the study include the following:

- The potential benefits to participants include personal satisfaction knowing

Version 10 Revised 11/21/2014

they have helped further research that could benefit patients with stroke and education about research studies.

- Further stroke patients could benefit from the treatment intervention in terms of increase ambulation and social well-being.
- Participants are not guaranteed a benefit from this study.

Data Safety and Monitoring

Data safety and monitoring will be performed in two ways. First, independent study monitoring will be performed by the Research Support Center at UAMS after the first 1-2 participants are enrolled. Thereafter, independent study monitoring will be performed by the Research Support Center at UAMS. Monitoring would occur according to the RSC monitoring plan. The Data and Safety Monitoring Plan describes operating procedures that will be in place to monitor compliance, study data validity and integrity, participant safety, individuals and/or entities (e.g., IRB) that will be involved in monitoring these procedures, and the frequency/regularity of this monitoring.

Adverse Events

Eliciting and Reporting Adverse Events:

Subjects will be monitored for the occurrence of adverse events throughout the study procedures.

Adverse Events Reporting and Evaluation:

All adverse events occurring during the course of the clinical study, whether device-related or otherwise, will be recorded on the Adverse Event CRF. For all adverse events, the study physician will provide an assessment of the adverse event, its treatment and resolution, and its relationship to the investigational device. All adverse events will be reported to the Sponsor and/or IRB in accordance with applicable institutional and federal regulatory guidelines.

Identification of Adverse Events:

An adverse event is defined as any new medical problem, or exacerbation of an existing problem, experienced by a subject while enrolled in the study, whether or not it is considered device-related.

Relationship of Adverse Events to the Study Device:

The study physician will assess the relationship of the adverse event to the investigational device. The relationship will be assessed using the following categories:

- Definitely Related: A direct cause and effect relationship between the investigational device and the adverse event exists.

- Possibly Related: A direct cause and effect relationship between the investigational device and the adverse event has not been clearly demonstrated, but is likely or very likely.
- Unlikely Related: A direct cause and effect relationship between the investigational device and the adverse event is improbable, but not impossible.
- Unrelated: The adverse event is definitely not associated with the investigational device.

Unanticipated Adverse Device Effects:

An unanticipated adverse device effect is defined as “any serious adverse effect on health or safety, or any life-threatening problem, or death caused by, or associated with, a device; if that effect, problem, or death was not previously identified in nature, severity, or degree of incidence in the investigational plan, or application (including supplementary application), or any other unanticipated serious problem associated with a device that relates to the rights, safety, or welfare of subjects.”

In the event unanticipated adverse effect occurs, the investigator will report the event(s) according to federal and institutional policies.

Serious Adverse Events:

Each adverse event will be assessed for its seriousness using the criteria outlined below. The term serious adverse event is not synonymous with a “severe” adverse event, which may be used to describe the intensity of an event experienced by the subject. An adverse event will be classified as serious if it meets any of the following criteria:

- Results in, or contributes to, a death
- Life-threatening (i.e., the subject was, in the opinion of the investigator, at risk of death at the time of the event, but it does not include an event that, had it occurred in a more severe form, might have caused death)
- Results in permanent disability or incapacity (i.e., permanent impairment of a body function or permanent damage to a body structure)
- Requires in-subject hospitalization or prolongs hospitalization
- Necessitates medical or surgical intervention to preclude a permanent disability or incapacity
- Results in a congenital anomaly or birth defect

Non-serious adverse events are all events that do not meet the criteria for a “serious” adverse event.

Severity:

Each adverse event will be assessed for its severity, or the intensity of an event experienced by the subject, using the following.

- Mild: Discomfort noticed, but no disruption to daily activity.
- Moderate: Discomfort sufficient to reduce or affect normal daily activity.
- Severe: Inability to work or perform normal daily activity.

Anticipated Adverse Events and Pre-existing conditions:

Pre-existing conditions will not be reported as an adverse event unless there has been a substantial increase in the severity or frequency of the problem which has not been attributed to natural history.

Data Handling and Recordkeeping

Each subject's name, birth date, address and phone number will be obtained for purposes of follow-up. We will ask for each subject's drug use history, medical history, and current drug use. Experimental data and questionnaire data will be collected. This information will be coded into the Microsoft Excel. Each subject's personal information will be de-identified in the database by using codes comprising the subject number and date and time the subject was tested. The PIs and study personnel at UAMS and UCA will have access to subject identities in order to arrange follow-up and to call them as part of the research project, such as follow-up contact. If subjects prefer e-mail correspondence research personnel will send e-mails for scheduling, follow-up, and research-related communication.

Data Analysis

Aims 1-3. Difference scores from baseline will be calculated for each outcome measure. A mixed model ANOVA with group (active tDCS groups versus sham tDCS) as the between subjects factor and time of assessment (pre, weeks 1-4, & one week and one month post) as the within subjects factor will be used to test all aims. A significant group effect, with active tDCS > sham tDCS, for any of the outcome measures would indicate that anodal tDCS augments gait training. A significant main effect of time would be evaluated using planned contrasts where we expect post treatment assessments to be improved relative to baseline. Interim analyses will be completed at critical stages during the protocol.

Power analysis: We aim to determine whether tDCS can augment the beneficial effect of gait training. Our preliminary study using tDCS to improve gait velocity and the SIS16 score yielded very large effect sizes for walking speed (2.95) and the SIS16 (1.32). In real terms, patients who received active tDCS reduced their time to walk 10 meters by about one minute (this could shave 5 minutes off a task, like getting mail, so it is functionally significant); whereas those who received sham reduced their time by only 10 seconds. Power calculations indicate that sample sizes = 11 will yield power of .95 and .80, respectively, to detect a tDCS-induced improvement gait velocity and physical function. However, assuming a very large effect size of greater than 2 is likely unrealistic. Therefore, we based our power analysis on determining a substantial meaningful change in gait speed (0.1 m/s) as determined by Perera et al.⁴⁸ Using a 2 x 3 mixed MANOVA with interaction and an estimated effect size of (Cohen's $d =$

Version 10 Revised 11/21/2014

0.39)³⁷, a conservative $r = 0.60$ ⁴⁹ and an alpha of 0.05 we will need 37 subjects per group to achieve a power of 85%. Therefore, we set our sample size at 88, so our study has sufficient power to detect meaningful changes in gait speed for individuals with chronic stroke.

We set our primary study sample size at 88, so our study has sufficient power to detect a benefit of gait training and to determine if tDCS augments improvement.

Exploratory Aim. We will classify patients as “likely responsive” and “likely unresponsive” to tDCS based on the magnitude of difference scores and compare them to determined patient characteristics that predict a treatment response. Predictors for 88 subjects include 1) NIH Stroke Scale score, 2) initial levels of impairment, 3) initial MT of the contralateral TA muscle (and recruitment curve parameters from the ipsilateral TA muscle), 4) initial SIS-16 total and subscale scores, 5) stroke laterality, and 6) modified Rankin Scale scores. A series of regression analyses will be conducted to reduce the overall number of predictors and to build an initial model, which assess the predictive value or weight of remaining variables, and to cross-validate predictors. To determine which stroke related variables are associated with a response to treatment, brain lesions will be mapped onto templates and analyzed using lesion subtraction techniques with the public domain MRIcro and MRIcron software programs (see Core B). Lesion subtraction will identify the lesion sites that are common to treatment responders and not common to nonresponders.

Ethical Considerations

This study will be conducted in accordance with all applicable government regulations and University of Arkansas for Medical Sciences research policies and procedures. This protocol and any amendments will be submitted and approved by the UAMS Institutional Review Board (IRB) to conduct the study.

The PI or designated staff will discuss the informed consent form with the subject volunteer. The consent process will take place in a quiet and private room. Subjects may take as much time as needed to make a decision about their trial participation and may take the document home if desired. The person obtaining consent will thoroughly explain each element of the document and outline the risks and benefits, alternate treatment(s), and follow-up requirements of the study. Participation privacy will be maintained and questions regarding participation will be answered. No coercion or undue influence will be used in the consent process. No research related procedures will be performed prior to obtaining informed consent. All signatures and dates will be obtained. A copy of the signed consent will be given to the participant. The informed consent process will be documented in each subject’s research record.

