Feasibility of obtaining valid TMS evoked recruitment curves for the TA muscle. In attempts to obtain recruitment curves for the TA muscle using a standard TMS coil, this study frequently exceeded stimulator output before the curve could become fully

established (i.e., plateau). In a series of normal subjects, this study overcame this limitation. First, by using a double cone coil which achieves deeper penetration of the magnetic field so TMS can be delivered at a lower intensity and, secondly, by having subjects make partial, isometric contractions of the TA muscle ipsilateral to stimulation (i.e., 20% of the maximum, volitional contraction: MVC). Contracting the ipsilateral limb enhances MEPs recorded from the contralateral limb (representative subject shown in Figure A, above). This method was then tested in normal subjects before, immediately following, and one hour after receiving active tDCS (10 [contact] anodal) or sham tDCS delivered over motor cortex. (representative subjects shown in B and C). MEP maximums increased after active tDCS for up to 1 hr and the recruitment curves became steeper indicating a lower threshold (i.e., an increase in cortical excitability). Similar changes were not seen for sham tDCS. During testing of our initial participants with stroke we found this technique to work for only one of three individuals. We will thus attempt to establish a motor threshold over the lesioned brain hemisphere for placement of tDCS electrodes and to establish participant characteristics for the exploratory regression analysis. Then we will obtain recruitment curves from stroke patients' intact hemisphere – having them contract the non-paretic, ipsilesional TA muscle at 20% MVC while a recruitment curve is obtained for the non-paretic, ipsilesional TA muscle. Additionally, we will assess the responsiveness of MEPs from the ipsilesional TA muscle after the administration of anodal tDCS to the lesioned cortex during our baseline assessments.

Feasibility of using tDCS with treadmill training in chronic stroke.

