In a pilot study investigating pairing locomotor training with transcranial direct current stimulation in patients with chronic stroke²³, our research collaborator at the University of Kentucky, [name], conducted a double-blind, randomized trial of active and sham tDCS (20 min at 2mA anodal stimulation over motor cortex) delivered just prior to locomotor training using a robotic gait orthosis treadmill. Eight participants (4 men, mean age=67.8; range=44-80) with chronic left hemisphere stroke (mean years post-stroke=4; range=1.1-11.6) were tested. Performance on a 10-meter walk test was the primary outcome measure, and assessments of functional ambulation category (FAC), timed up and go, balance, and the 16 item Stroke Impact Scale (SIS 16) were secondary measures. Improvement on the 10-meter walk test and the SIS 16 following active tDCS are shown in the figure - right. Active tDCS lead to greater improvement than sham tDCS on the FAC ($p=0.028$) and similar trends were evident for the SIS 16 ($p=0.062$) and the timed up and go test ($p=0.066$). This study shows that active tDCS augments gait training and function. The data were also used for power calculations.

Hypothesis and Specific Aims

Hypothesis: Increasing cortical excitability with active anodal tDCS prior to gait training will augment recover from a stroke.

Specific Aims:

1. Determine if active tDCS augments gait. Gait speed is a primary outcome measure. Spatiotemporal and kinematic gait assessment are secondary measures of gait. Over ground laboratory assessments of gait will measure 1) gait velocity and spatiotemporal gait measures using the GAITRite electronic walkway 2) ankle, knee, and hip angles using the SIMI motion analysis system. Changes in gait parameters will be expressed as difference scores from baseline. Difference scores will be compared between the active and sham groups to determine if tDCS augments gait parameters.

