2. Determine if active tDCS augments cortical excitability after gait training. Cortical excitability will be defined by a cortical recruitment curve, a primary outcome measure, derived from plots of motor evoked potentials (MEPs) recorded from the ipsilesional TA muscle. MEPs are elicited by single pulse transcranial magnetic stimulation (TMS) delivered at increasing intensity over motor cortex. Changes in the slope of the recruitment curve signal change in cortical excitability. Difference scores from baseline will be compared between active and sham groups to determine if tDCS augments cortical excitability after FESAGT. A repeat fMRI will be performed to assess change in cortical excitability after gait training.
3. Determine if active tDCS augments physical function and social wellbeing. The Stroke Impact Scale-16 (SIS-16), a primary outcome measure, will be used to assess ADL/IADL, mobility, and social and occupational engagement at baseline and post treatment assessments. Difference scores from baseline will be compared between active and sham groups to determine if tDCS augments physical function and social well-being.

Exploratory Aim

Identify patient characteristics that predict response to treatment. Patients will be classified empirically based on their response to treatments. Regression analyses will examine whether and how initial impairment, functional level, and cortical excitability predict a treatment response.

Study Interventions

tDCS and gait training will be conducted at UCA three times a week for 4 consecutive weeks

Version 10 Revised 11/21/2014

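### The any-outcome rule in Data Analysis lets the Aim 2 recruitment-curve slope, taken from the intact hemisphere, stand alone as evidence that tDCS augments gait training

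*Combined protocol and SAP*

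**What the plan says.** Data Analysis, under Aims 1-3, applies one mixed-model ANOVA to all aims and gives a single rule for reading it: "A significant group effect, with active tDCS > sham tDCS, for any of the outcome measures would indicate that anodal tDCS augments gait training". The Power analysis is built on gait speed, but no section ranks the outcomes or narrows that rule.

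Specific Aims names three primary outcomes. For Aim 1, "Gait speed is a primary outcome measure". For Aim 2, the recruitment curve is "a primary outcome measure, derived from plots of motor evoked potentials (MEPs) recorded from the ipsilesional TA muscle". For Aim 3 it is the SIS-16. Aim 2's own comparison is narrower than the rule. Its difference scores are compared "to determine if tDCS augments cortical excitability after FESAGT", the last word being read here as the gait training, in line with the aim's title. The Hypothesis makes excitability the means and recovery the end: "Increasing cortical excitability with active anodal tDCS prior to gait training will augment recover from a stroke".

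The side is set out elsewhere:

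- **Preliminary studies** says the team will take "recruitment curves from stroke patients' intact hemisphere", using the non-paretic, ipsilesional TA. The method had been tried in the first participants with stroke, and "we found this technique to work for only one of three individuals". The same paragraph plans a baseline check of how MEPs from that muscle respond after anodal stimulation of the lesioned cortex.
- **Study Interventions** puts the anode over the leg area of the lesioned hemisphere and the cathode over the opposite motor cortex.
- **Background and Rationale** says anodal stimulation raises excitability and cathodal stimulation lowers it, for about 30 to 90 minutes beyond the stimulation.

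**The concern.** The rule converts a finding about one thing into a conclusion about another. The slope is a physiological measure on the non-paretic side. Gait training is augmented, in the ordinary sense, when gait improves. Under the rule as written, a trial with no difference in gait speed and a steeper intact-side slope in the active group could report that anodal tDCS augments gait training.

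The side makes the inference weaker still. A reader would naturally take a positive Aim 2 result as the anode raising excitability in the lesioned cortex, which is the hypothesised route to recovery. This slope does not record that cortex. The plan does not say what a rise or a fall on the cathode side would mean for its mechanism.

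**Working it through.** **1. Which hemisphere the slope reflects.** The ipsilesional leg is the non-paretic leg. Its curve is obtained from the intact hemisphere (Preliminary studies). The anode is over the lesioned side, so the cathode, over the opposite motor cortex, is over the intact side (Study Interventions). The slope is therefore a cathode-side measure.

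**2. What direction the documents support.** Aim 2 and the rule both look for an increase. The support given is that "MEP maximums increased after active tDCS for up to 1 hr and the recruitment curves became steeper". Those were normal subjects, followed for up to about an hour after anodal stimulation over motor cortex; the text describes no cathode-side curve. The polarity statement in Background would, if anything, suggest a fall under the cathode during and shortly after stimulation. The outcome curves are taken at weeks 5 and 8, after treatment ends, so that statement does not settle the direction then.

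**3. What the rule concludes.** Aim 2 alone gives a statement about excitability. The rule in Data Analysis gives a statement about gait training. The second does not follow from the first.

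**4. Size when the slope truly rises and gait does not.** The plan gives no figure for this, so there is none to reproduce. Inputs: 44 per group (Study Population) and alpha 0.05 (Power analysis; sidedness not stated, two-sided assumed). The slope effect d is assumed, in standard deviations of the quantity compared between groups. The value 0.39 is the effect size the Power analysis uses for gait speed and serves only as a reference point.

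Probability of a significant slope result favouring active = Φ(d × √(44/2) − 1.96), with √22 = 4.690.

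| Assumed d | d × 4.690 − 1.96 | Probability |
|---|---|---|
| 0.2 | −1.022 | 15% |
| 0.39 | −0.131 | 45% |
| 0.5 | 0.385 | 65% |
| 0.8 | 1.792 | 96% |

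These count the slope only. The 2.5% chance of a false positive on gait speed itself is left out.

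**5. Separate quantity: false claims when tDCS changes nothing.** Each two-sided 0.05 test has a 0.025 chance of a false result favouring active.

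- Gait speed only: 2.5%.
- Any of the three primaries, independent: 1 − 0.975³ = 7.3%.
- With equal positive correlation among the three (assumed, as none is given), simulation at 44 per group gave 6.8% at 0.3, 5.8% at 0.6 and 4.2% at 0.9. The ceiling under any correlation is 3 × 0.025 = 7.5%.

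**6. Why the remedy must name gait speed.** If the claim rested on any gait outcome, speed plus ankle, knee and hip angles would give 1 − 0.975⁴ = 9.6% if independent, which is more than the three-primary rule.

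**The case against.** The strongest reply is that the aims already say what each comparison determines: gait, excitability, function and well-being. On that view the fault is one loose summary sentence. This is largely right, and it is why the remedy is small. But the sentence is the plan's only stated criterion for a tDCS effect, it says any outcome, and nothing overrides it.

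Several stronger readings are tempting, and the documents do not support them:

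- **That the wrong hemisphere is measured.** The choice is disclosed and rests on feasibility. The mechanism in Background involves links between hemispheres, so the intact side is relevant.
- **That the hemisphere is never named.** Preliminary studies names it. The label is missing from Aim 2, Outcome Measures and Data Analysis, although Aim 2 does name the ipsilesional muscle.
- **That looking for a rise contradicts the cathodal effect.** The stated effect lasts 30 to 90 minutes, and the curves come at weeks 5 and 8. The planned baseline check also shows that the investigators meant to examine how this side responds. There is tension, not contradiction.
- **That a slope change cannot be due to the anode.** A randomised active-sham difference reflects both electrodes together. The design cannot separate them, so ruling the anode out is as unsupported as crediting it.
- **That 7.3% is the size of this defect.** It is generic multiplicity and would be the same for any three outcomes, whichever hemisphere was recorded.

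**Conclusion.** The concern holds for the decision rule. As written, a rise in intact-hemisphere slope alone, with gait speed unchanged, meets the plan's criterion for a gait-training benefit. If such a rise is real, the chance of the unsupported gait claim equals the power of the slope test: about 15% to 96% across assumed effects of d = 0.2 to 0.8. Multiplicity adjustment alone would not cure this, because the slope finding would be true and only its label wrong. Under a global null the any-of-three rule gives about 7.3% false claims favouring active if the outcomes are independent, against 2.5% for gait speed alone.

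These figures assume two-sided testing at 0.05, 44 analysed per group and a single group contrast per outcome. Only the three named primaries are counted. The textual conclusion needs none of these assumptions. The gait-speed and SIS-16 analyses themselves are not affected. This should be fixed, but it does not invalidate the design.

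**What to change.** In Data Analysis, replace the any-outcome sentence with one conclusion per aim, for example: *Active tDCS will be said to augment gait training only if the group effect on gait speed is significant and favours active tDCS; other gait measures are supportive. The recruitment-curve slope supports only a statement about intact-hemisphere excitability. The SIS-16 supports only the Aim 3 conclusion.*

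In Specific Aims (Aim 2) and Outcome Measures (Study Aim 2):

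- Repeat the intact-hemisphere label from Preliminary studies.
- State in advance the direction of slope change expected on that side and how a rise and a fall will each be read, referring to the planned baseline check of ipsilesional-TA MEPs.
- Describe any slope difference as an effect of the active montage, not as evidence of raised excitability in the lesioned cortex.

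Do not rely on post-treatment motor threshold from the lesioned side to fill that gap. Preliminary studies promises only an attempt, for electrode placement and participant characteristics, and Baseline Procedures lists it at baseline. Its collection at weeks 5 and 8 can only be inferred from a cross-reference to the recruitment-curve procedure.

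The cost is wording in three sections, with no new visit, test or participant. The Aim 2 claim becomes narrower. No change to stimulation is proposed.
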